Blocks of pain will be administered with an adaptation of an established heat/capsaicin model (27). First, 1% capsaicin cream will be applied to a 40 x 40 mm region of skin 12 cm away from the wrist on the right volar forearm. After 30 minutes, the capsaicin cream will be cleaned off and cutaneous heat stimuli will be applied via the Medoc Pathway System using a 30 x 30 mm ATS thermode. Pain ratings will be assessed by administering 22 s blocks of pain at a temperature that each participant reports at baseline to be 7 out of 10 on a pain visual analog scale. This temperature, individualized for each participant at baseline using the PEST procedure, will be administered throughout the experiment. Studies have shown that stimuli rated as 7 out of 10 produce highly reproducible results in terms of pain ratings and fMRI activation without posing significant risk to participants (28). The device will be set to stop heating at 51.5° C to avoid tissue damage. After each heating trial, participants will rate the intensity of the pain from 1-10. The temperature rated as "7 out of 10" at baseline will be administered 12 times during the baseline scan, 12 times during the scan following sham LIFUP and 12 times during the scan following real LIFUP. These procedures have been used previously in IRB-approved studies.

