10.3. Magnetic Resonance Imaging (MRI). A Siemens 3T Trio MRI scanner will be used for imaging. After QST testing, the MR compatible ATS thermode will be placed on the capsaicin-treated right volar forearm. Participants will undergo standard high-resolution anatomical scans prior to undergoing functional scans during which 22 second blocks of heat will alternate with 22 second blocks of rest. These heat stimuli were previously rated as "7 out of 10" in intensity during baseline testing. Each fMRI scan will involve 12 pain/rest blocks. At the end of the functional scan, each participant will rate the intensity of the pain that they experienced. The functional pain/rest scan will be repeated three separate times throughout the experiment: (1) at baseline, (2) after 20 min of sham LIFUP, and (3) after 20 min of real LIFUP. A short interleaved LIFUP-fMRI scan will be performed immediately before the pain/rest block scans after sham LIFUP and real LIFUP. During these sessions, the LIFUP machine will fire single pulses at 1Hz frequency. A TR delay will be used to minimize LIFUP-induced destruction of acquired scan data. E-Prime software will be used to trigger LIFUP pulses and coordinate them with scanner TR delays. The purpose of the interleaved LIFUP-fMRI sequence is to examine how LIFUP affects BOLD signal changes in real time.

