12.0 Data Management

The behavioral pain measures will be examined using a repeated measures ANOVA with time and condition (LIFUP, sham) as between group variables. These will be paired data within each subject.

Justification of Sample Size: Prior studies by our group using this same paradigm have shown differences in pain intensity with prefrontal TMS, or blocking of opiates. (29)

Consent procedures will be carried out within a private room inside the IOP. Data acquisition will be performed within the MUSC CBI research scanner at [name] The data will not be labeled with identifiable information. Participants will be identified on all research records solely by a number, ensuring confidentiality of all data. Any information that is obtained in connection with this study and that could identify the participants will remain confidential and will not be released or disclosed without their further consent, except as specifically required by law. If the results of this research are presented at scientific meetings, participant identity will not be

disclosed. All conversations with participants will take place behind closed doors in front of only the participant and designated caregivers, family, or friends.

Any imaging or other research data will be stored in a de-identified manner.

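### Pain ratings have one shared baseline scan and no named period term; the real-minus-sham difference adjusted for period should be the stated contrast

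*Combined protocol and SAP*

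**What the plan says.** Section 4.1 makes pain ratings to thermal stimuli the primary endpoint, without naming the task, skin site or contrast. Section 10.2 describes two behavioural measures. QST on untreated skin yields temperatures and is done before and after each scanning block. The heat blocks on capsaicin-treated skin yield ratings, so they fit the wording of 4.1 best.

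For those blocks, 10.3 states: "The functional pain/rest scan will be repeated three separate times throughout the experiment: (1) at baseline", the other two scans being after sham and after real LIFUP. Section 10.2 gives the same count: the calibrated temperature "at baseline will be administered 12 times during the baseline scan, 12 times during the scan following sham LIFUP and 12 times" in the scan after real LIFUP.

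On preparation, 10.2 says "First, 1% capsaicin cream will be applied to a 40 x 40 mm region of skin" and then "After 30 minutes, the capsaicin cream will be cleaned off". On the stimulus it says: "This temperature, individualized for each participant at baseline using the PEST procedure, will be administered throughout the experiment". It describes neither a second application nor a recalibration.

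Section 10.1 places both conditions in one session in counterbalanced order. Section 12.0 analyses the behavioural pain measures with a "repeated measures ANOVA with time and condition (LIFUP, sham") and calls these factors between-group, although the next sentence says the data are paired within subject. It does not define time and names no period or sequence term.

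**The concern.** A before/after-by-condition analysis needs four cells per participant: before and after real, before and after sham. QST fills all four. The ratings fill three, because one baseline must serve both conditions, and that baseline is always the earliest scan.

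The test temperature is fixed once, on skin whose capsaicin sensitisation may fade, and repeated heat may itself raise or lower ratings. By the last scan the participant has had 24 earlier heat blocks. Any such drift appears in change from baseline. Aim 2 asks how large LIFUP-induced analgesia is, and 12.0 does not say which term or contrast answers that question. With no period term, drift between the two post-LIFUP scans also goes into the error of the real-versus-sham comparison.

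**Working it through.** The plan has no figure of its own to reproduce here. It gives no SD, effect size, alpha or power for the ratings, and the number of subjects is 35 in section 6.0 but twenty in 10.1. Drift and SD below are assumptions.

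**Elapsed time.** A scan has 12 blocks of 22 s heat and 22 s rest (10.3): 12 × 44 s = 528 s = 8.8 min. Rest is 20 min (10.1). LIFUP blocks last 10 min in 10.1 and 20 min in 10.3. The third scan starts, counted from the start of the baseline scan, at:

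| | 10-min blocks | 20-min blocks |
|---|---|---|
| Rest counted from end of LIFUP | 8.8 + 10 + 20 + 10 = 48.8 min | 8.8 + 20 + 20 + 20 = 68.8 min |
| Rest counted from end of second scan | 8.8 + 10 + 8.8 + 20 + 10 = 57.6 min | 8.8 + 20 + 8.8 + 20 + 20 = 77.6 min |

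QST and the interleaved scan would add to these.

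**What the shared baseline does.** (real − baseline) − (sham − baseline) = real − sham, so the baseline cancels and the condition effect stays estimable. If the baseline is entered twice in a before/after-by-condition ANOVA:

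- the interaction equals real − sham;
- the condition main effect is (real + baseline)/2 − (sham + baseline)/2, which is half of real − sham;
- the time main effect is (real + sham)/2 − baseline, which is drift, plus any placebo effect, plus half the LIFUP effect.

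**Drift in change from baseline.** With a drift of d points per scan and balanced order, each condition sits half the time at scan 2 (drift d) and half at scan 3 (drift 2d). The mean is (d + 2d)/2 = 1.5d in both conditions: about 0.4, 0.75 and 1.5 points for d = 0.25, 0.5 and 1.0.

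**Drift in real minus sham.** The bias is (n real-first − n sham-first)/N × (drift at scan 2 − drift at scan 3). For drift of −1 then −2 points this is 0.00 with 10/10, 1/35 = +0.03 with 18/17 and 5/35 = +0.14 with 20/15. It would reach −1.0 only if real always came second.

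**Precision without a period term.** Half the paired differences shift by +d and half by −d, so their variance is multiplied by 1 + d²/SD². With an assumed paired-difference SD of 1.5:

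- d = 0: no inflation
- d = 0.25: 1 + 0.0625/2.25 = 1.03
- d = 0.5: 1 + 0.25/2.25 = 1.11
- d = 1.0: 1 + 1/2.25 = 1.44

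**Simulation.** 20,000 replicates; within-subject SD 1.0 (paired-difference SD √2 ≈ 1.41), between-subject SD 1.5, two-sided 0.05, no carryover, all assumed. The power columns take a true LIFUP effect of −1 point.

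| N (order split) | Drift at scans 2/3 | Type I, real vs sham, no period | Type I, with period | Type I, real vs baseline | Power, no period | Power, with period |
|---|---|---|---|---|---|---|
| 20 (10/10) | 0/0 | 0.050 | 0.051 | 0.05 | 0.85 | 0.85 |
| 20 (10/10) | −0.5/−1 | 0.039 | 0.052 | 0.61 | 0.82 | 0.85 |
| 20 (10/10) | −1/−2 | 0.017 | 0.050 | 0.99 | 0.71 | 0.84 |
| 35 (18/17) | 0/0 | 0.051 | 0.050 | 0.05 | 0.98 | 0.98 |
| 35 (18/17) | −0.5/−1 | 0.038 | 0.049 | 0.85 | 0.97 | 0.98 |
| 35 (18/17) | −1/−2 | 0.018 | 0.048 | 1.00 | 0.94 | 0.98 |

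**The case against.** The best defence is that the design already deals with drift where it matters. The condition factor in 12.0 has two levels, LIFUP and sham, and 10.1 counterbalances their order, so drift falls equally on both. Omitting period makes that test conservative; it does not create false analgesia. This stands. A reader might infer from the single early baseline that drift will be taken for analgesia. The documents do not support that for real versus sham. The high error rates belong to real versus baseline, which the plan nowhere names as its test.

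A reader might also infer that change cannot be derived for the ratings. It can: each condition's change from the common baseline is computable, and the difference between the changes is real minus sham. What is missing is a separate pre-treatment rating for each condition.

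Time is undefined, so the misfit depends on reading it as before/after. Read as trial within scan, it gives a complete 12 × 2 layout; read as first or second block, it would itself be a period factor. This also stands, but the plan does not say which it means.

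No drift rate is documented, and 10.2 asserts that stimuli at the chosen intensity give reproducible ratings. Drift may therefore be small, and at 0.25 to 0.5 points per scan the variance cost is only 3–11%.

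Finally, the single capsaicin application is inferred from silence and from the one-session text of 10.1, which 16.0 supports by speaking of one scan. Sections 5.0 and 7.0 describe scanning-related procedures at Visits 2 and 3. If the conditions fall on separate visits, the elapsed times and the 24 earlier blocks need not apply, and one baseline scan would leave a visit without any.

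**Conclusion.** The point holds as one of specification and precision. The ratings have one shared baseline, always first. The ANOVA in 12.0 does not fit them if time means before/after, mislabels a within-subject factor as between-group, and names no period term.

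With order balanced or nearly so and no carryover, the mean real-minus-sham difference is free, or almost free, of drift. The cost is a variance inflation of 0% to 44% over the assumed drifts of 0 to 1 point per scan at an assumed SD of 1.5. In the simulation, power fell at worst from 0.85 to 0.71 with 20 subjects and from 0.98 to 0.94 with 35.

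Change from the single baseline is a different matter: it carries an average drift of 1.5d in both conditions plus any placebo effect, so on its own it does not give the magnitude that Aim 2 asks for. Carryover after the rest period is a separate question that neither counterbalancing nor a period term settles.

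**What to change.** In section 12.0:

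- For pain ratings, define the primary contrast as the within-subject difference between the post-real and post-sham scans, with condition as a within-subject factor and period (first or second LIFUP block) in the model.
- Show change from the shared baseline descriptively, beside the sham comparison, and do not interpret it alone as LIFUP-induced analgesia.
- Keep the before/after-by-condition layout for QST, where all four values exist, and define time there.
- Record minutes since capsaicin removal at each scan.

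The one-session text in 10.1 must be reconciled with the two scanning visits in 5.0 and 7.0, and the 10-min blocks in 10.1 with the 20-min blocks in 10.3, because the number of baselines and the elapsed times depend on them.

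The contrast and period term cost some wording, one degree of freedom and one clock time per scan. They require no change to procedures or sample size, and in the simulation they held type I error at 0.048–0.052 at every drift tried.

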12.0 Data Management

The behavioral pain measures will be examined using a repeated measures ANOVA with time and condition (LIFUP, sham) as between group variables. These will be paired data within each subject.

Justification of Sample Size: Prior studies by our group using this same paradigm have shown differences in pain intensity with prefrontal TMS, or blocking of opiates. (29)

Consent procedures will be carried out within a private room inside the IOP. Data acquisition will be performed within the MUSC CBI research scanner at [name] The data will not be labeled with identifiable information. Participants will be identified on all research records solely by a number, ensuring confidentiality of all data. Any information that is obtained in connection with this study and that could identify the participants will remain confidential and will not be released or disclosed without their further consent, except as specifically required by law. If the results of this research are presented at scientific meetings, participant identity will not be

disclosed. All conversations with participants will take place behind closed doors in front of only the participant and designated caregivers, family, or friends.

Any imaging or other research data will be stored in a de-identified manner.

12.1. fMRI Data Analysis: Individual fMRI Data Analysis (first level analysis): The fMRI data will be analyzed blind to LIFUP activation. MR scans will be transferred into ANALYZE format with MRICro (<http://www.sph.sc.edu/comd/orden/mircro.html>) and then further processed in Matlab 7.3 (Mathworks, Sherborn, MA) with Statistical Parametric Mapping software 12 (SPM12, The Wellcome Department of Cognitive Neurology, London, <http://www.fil.ion.bphf.ac.uk>). Default settings were used unless indicated otherwise. All volumes will be realigned to the first volume. After realignment, for all subjects, movement across the 8 minutes scan must be less than 0.5 mm in 3 axes and less than 0.5 degree in 3 orientations. The images will be normalized stereotactically into a standard space with a resolution of 3 mm³ voxels using the averaged functional EPI image – the Montreal Neurological Institute (MNI) EPI template in SPM12. Subsequently, the data will be smoothed with an anisotropic 8 mm³ Gaussian kernel and high-pass filtered (cut-off period=128s). In a first level of statistical analysis, using a boxcar function convolved with the modeled hemodynamic response function as the basic function for the general linear model, we will obtain contrast-maps of the difference between task and rest for each subject. The six head movement parameters will be included as confounds.

Group Data Analysis (the second level analysis): Subject-specific contrasts will be entered into a second-level analysis to obtain a random effect analysis of activation effects across the entire group. The combined group *t* maps will be thresholded at $p \leq 0.05$ corrected for multiple comparisons (family-wise error, FWE) and cluster analyses will be performed with a spatial extent threshold of 5 voxels.

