5.0 Inclusion and Exclusion Criteria/Study Population

Screening Procedures. Prospective subjects (self-referred via flyers, e-mail announcements, and Catalyst advertisements) will be interviewed by the research team over the phone. Questions asked during this phone interview will focus on chronic (and current) medical problems, seizure history, medications, psychiatric disorders, substance abuse, magnetic resonance imaging eligibility and pain history. The inclusion/exclusion criteria will be used to screen-out participants with conditions that might interfere with or confound the research, or that might render participants vulnerable to potentially negative effects of the

laboratory pain procedures. A copy of the screening form is uploaded to the eIRB website. If the participant qualifies for the study and wishes to proceed, then he or she will be invited to a screening visit that will take place in a quiet office in the Institute of Psychiatry. The research procedures, risks and benefits will be explained during this visit. After providing written informed consent to participate, if the participant is female, then she will also receive a pregnancy test. Participants will be paid **\$30** for participating in the screening procedure. Participants meeting inclusion criteria will be invited to participate in the laboratory investigation. If they choose to participate, they will be paid **\$120** for Visit 2 scanning session and **\$120** for Visit 3 scanning session for a total of **\$270**.

Selection Criteria. Participants must meet the following criteria: (1) 18-45 years of age, (2) no seizure history (individual or family), (3) no history of depression, (4) no hospitalizations or surgeries in the previous 6 months, (5) not currently experiencing pain, (6) no history of chronic pain, (7) no metal implants or objects (e.g. pacemakers, metal plates, wires), (8) not pregnant, (9) no alcohol dependence (10) no illicit drug use in the previous 6 months, (11) no known allergy to capsaicin, (12) no history of brain surgery or brain lesions, (13) no history of loss of consciousness (greater than 15 min), (14) no stimulants or medications that lower seizure threshold.

6.0 Number of Subjects – 35

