7.0 Setting

The initial screening, interview, and structural scan (Visit 1) will be on the Center for Biomedical Imaging at [name]. For Visit 2 and 3, the Brainsight targeting will occur on at the Brain Stimulation Lab on the 5th floor of the Institute of Psychiatry. The LIFUP-MRI scanning will be done at [name]

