10.0 Study Design/Methods

10.1. Study Design. Twenty healthy volunteers between 18-65 years of age without history of depression or chronic pain will be recruited to participate in this sham-controlled, double-blind crossover study, all within one session within the MRI scanner. All participants will receive 10 minutes of sham LIFUP, 20 minutes of rest, and 10 minutes of real LIFUP within the MRI scanner using the BXPulsar 1001, Brainsonix Inc. The order will be counterbalanced. The duration of the LIFUP analgesia and BOLD effects will be determined.

10.2. Behavioral Measures. We will begin baseline pain assessments by administering cutaneous hot and cold stimuli via the Medoc Pathway System (Medoc, Durham, NC) using a 30 x 30 mm ATS thermode. There will be two behavioral measures: quantitative sensory testing (QST) on untreated skin and blocks of pain on capsaicin-treated skin.

QST will be done using method of limits testing on the thenar eminence of the right hand. A program will be set up to administer 10 hot stimuli with random durations between each trial. The ATS thermode begins at 32°C and increases by 0.5°C per second. Participants will be asked to press a button in order to signify three different measures: (1) sensory threshold, or the temperature at which the stimulus becomes noticeable, (2) pain threshold, or the temperature at which the stimulus becomes painful, and (3) pain tolerance, or the temperature at which the stimulus becomes too painful to tolerate. Measuring these thresholds will yield information about

A β , A δ , and C fibers, respectively. The device will be set to stop heating at 51.5° C and stop cooling at 0° C to avoid tissue damage. These ten trials will be performed once before and once after each scanning block, either with thalamic LIFUP or 'fake' thalamic LIFUP.

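### Section 12.0 labels time and condition as between-group factors in a paired crossover; they should be specified as within-subject factors, with period and the unit of analysis stated

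*Combined protocol and SAP*

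**What the plan says.** Section 12.0 states the behavioral analysis in one sentence: "The behavioral pain measures will be examined using a repeated measures ANOVA with time and condition (LIFUP, sham) as between group variables". The sentence after it says: "These will be paired data within each subject".

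Section 10.1 describes a "double-blind crossover study, all within one session within the MRI scanner". It continues: "All participants will receive 10 minutes of sham LIFUP, 20 minutes of rest, and 10 minutes of real LIFUP within the MRI scanner". On sequence it says: "The order will be counterbalanced".

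Section 10.2 has two kinds of behavioral measure. For quantitative sensory testing (QST): "These ten trials will be performed once before and once after each scanning block". For the capsaicin heat blocks, each scan has 12 stimuli with a 1-10 rating after each one; section 10.3 also has one rating at the end of the functional scan. Section 10.2 lists a single baseline scan.

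On visits, section 5.0 pays separately for Visit 2 and then "for Visit 3 scanning session for a total of" $270 including screening. Section 7.0 says: "For Visit 2 and 3, the Brainsight targeting will occur on at the Brain Stimulation Lab".

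**The concern.** In a crossover where each participant has both conditions, condition is a within-subject factor, and so is any sensible version of time. The LIFUP-sham difference should be judged against the variability of differences within a person. Calling the factors between-group puts stable differences between people into the error term. In a study of 20 or 35 healthy volunteers, that gives up the main advantage of the crossover.

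Changing the label alone would leave some of the analysis open. Time is not defined: it could be before and after a block (QST), trial within scan, baseline against post-stimulation, or scan order. Period (first or second stimulation) is in the model only if time means scan order. Per-trial and end-of-scan ratings are both described, without a statement of which is analysed. Whether there is one session or two determines what the period and baseline terms are: a single shared baseline cancels from the LIFUP-minus-sham difference, while a separate baseline at each visit does not.

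**Working it through.** **Inputs from the document.** n=20 (section 10.1) and n=35 (section 6.0), which disagree, so both were used; 12 ratings per scan (section 10.2). The plan gives no figure to reproduce: no effect size, SD, correlation or power, and a 0.05 level only for the fMRI maps (section 12.1).

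**Assumptions.** Two-sided 5% test; 80% power for the correct paired test; correlation ρ between a participant's sham and LIFUP scan means of 0.3, 0.5 or 0.7.

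**Step 1: the error term.** If each scan mean has variance σ², the true variance of a LIFUP-sham difference is 2σ²(1−ρ). A between-group test uses 2σ². The ratio of true to assumed variance is 1−ρ, so the test is too strict for any ρ above 0 and correct at ρ=0. In large samples its type I error is 2[1−Φ(1.96/√(1−ρ))], which is 1.9%, 0.56% and 0.03% at ρ = 0.3, 0.5 and 0.7.

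**Step 2: the two sample sizes.** The standardized paired difference that gives 80% power is 0.660 at n=20 and 0.487 at n=35. Simulating correlated pairs and applying the independent-groups test gives:

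| ρ | Type I error, n=20 | Power, n=20 | Type I error, n=35 | Power, n=35 |
|---|---|---|---|---|
| 0 | 5.0% | 82% | 5.0% | 81% |
| 0.3 | 2.1% | 70% | 2.0% | 69% |
| 0.5 | 0.7% | 54% | 0.7% | 53% |
| 0.7 | 0.1% | 27% | 0.1% | 24% |

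The ρ=0.5 type I error at n=20 was 0.7% to 0.8% across runs. The paired test stayed at about 5% type I error and 80% power throughout.

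**Step 3: when the test could be too lenient.** This needs a different model, in which all single ratings are entered as independent observations. With participant SD P, scan-level SD s and residual SD e, the expected mean squares are 12s²+e² for condition and P²+s²+e² for error. They are equal when 11s² = P², so s = P/√11 = 0.30P. Below that the test is too strict, and above it too lenient, whatever e is. With P = e = 1 and n=20, type I error is about 0.7%, 3.5% and 14.8% at s = 0, 0.25 and 0.5, and about 35% at s = 1, so no one value is a ceiling.

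For s = 0 to 0.5 in the same model, treating trials as the repeated factor with condition between groups gives type I error of 0.0% to about 0.05%. The scan-mean correlation there is P²/(P²+s²+e²/12): 1/1.083 = 0.92 at s=0 and 1/1.333 = 0.75 at s=0.5. These cases lie outside the ρ range of Step 2 and should not be set beside it as one scenario.

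**Step 4: period.** With order balanced and period not modelled, a period effect of 0.25, 0.5 or 1.0 SD of the paired differences lowers 80% power to 78%, 72% and 50% at n=20. Modelled, power stays at about 80%.

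**The case against.** The strongest reply is that no competent analyst would follow the label. The sentence itself says repeated measures, the next one says paired, and section 10.1 says crossover. If both factors really were between-group, nothing named would remain as the repeated factor. This stands: the likely defect is a mislabel with missing detail, not an intention to analyse the data unpaired. It does not make the sentence harmless, because it is the only statement of the behavioral analysis and it contradicts the one after it.

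A reader might infer that the plan inflates type I error. The documents do not support that. Inflation requires treating single ratings as independent, which ignores the repeated-measures wording, and then a scan-level SD above about 0.30 of the participant SD. With trials kept as the repeated factor, the test as labelled errs only toward strictness when scan means are positively correlated.

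A reader might also infer that the primary contrast is free to be chosen after the data are seen. That goes too far. Section 12.0 names the LIFUP-sham comparison and section 4.1 labels pain ratings as primary. The mentions of tolerance (section 1.0) and threshold (section 3.0) are a hypothesis and a procedural description, and neither is called primary. What does remain open is which rating is analysed.

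Finally, a correctly labelled within-subject ANOVA would by itself cure the error term; period adjustment is a refinement. That is also right, but it is nearly free.

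**Conclusion.** The point holds as a specification error that should be fixed. The between-group label contradicts the design and the plan's own next sentence. Followed as a repeated measures ANOVA with condition between groups, it makes the LIFUP-sham test too strict. The loss is from an assumed 80% power to about 70%, 54% or 27% at n=20 for correlations of 0.3, 0.5 or 0.7, and it is nearly the same at n=35. These sizes rest wholly on the assumed power and correlations; the direction needs only a positive correlation between a person's scan means. If the analyst reads the label as a slip and runs the paired analysis, the loss does not occur. The visit-structure and duplicate-rating questions are separate clarifications, to be settled in the same edit because the model terms depend on them; they do not add to the seriousness of the error-term point.

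**What to change.** Replace the analysis sentence in section 12.0 with:

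> Condition (LIFUP, sham) and time are within-subject factors. LIFUP and sham are compared by the within-participant difference in one summary per condition (for ratings, the mean of the per-trial ratings in the scan, or the single end-of-scan rating if that is the one chosen; for each QST measure, the after-block mean minus the before-block mean), adjusted for period (first or second stimulation). Any trial-level mixed model includes participant and participant-by-scan (QST: participant-by-block) random effects.

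The second random effect is needed. For ratings at n=20 with participant and residual SD 1 and scan SD 0, 0.25 and 0.5, a participant effect alone gives type I error of 5.1%, 13.2% and 30.0%. Adding participant-by-scan gives 3.8%, 4.8% and 5.1%, and period-adjusted paired scan means give 5.2%, 5.1% and 5.1%. QST has two sets of trials per condition, so its term must be at block level: with participant and participant-by-condition effects but no block effect, type I error is 4.9%, 11.8% and 26.3% at block SD 0, 0.25 and 0.5.

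In the same edit:
- define time separately for QST and for ratings (if it means scan order, period is already in the model);
- state which rating is collected and which is analysed;
- reconcile the single session in section 10.1 with Visits 2 and 3 in sections 5.0 and 7.0.

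**Cost.** One reworded paragraph, these statements, and no new data. Period uses one degree of freedom: with no period effect, power goes from 80.0% to 79.8% at n=20 and to 79.9% at n=35.

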4.0 Study Endpoints – Overall we will test whether thalamic LIFUP during a pain provocation is safe and feasible. In addition, we will test the following endpoints.

4.1. Primary endpoint: Thalamic LIFUP will modulate pain ratings measured by administering cutaneous hot and cold stimuli via the Medoc Pathway System.

4.2. Secondary endpoints: Thalamic LIFUP will reduce BOLD activity in the thalamus.

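### Order of real and sham is counterbalanced, but the pain ANOVA names no period or sequence term, leaves 'time' undefined and calls paired factors between-group, so power may be lost on the capsaicin-heat ratings

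*Combined protocol and SAP*

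**What the plan says.** Section 10.1 describes a "sham-controlled, double-blind crossover study, all within one session within the MRI scanner". On timing it says "All participants will receive 10 minutes of sham LIFUP, 20 minutes of rest, and 10 minutes of real LIFUP", and then "The order will be counterbalanced". There are therefore two sequences, real first and sham first. The numbers per sequence are not given.

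Section 4.1 makes pain ratings the primary endpoint: "Thalamic LIFUP will modulate pain ratings measured by administering cutaneous hot and cold stimuli via the Medoc Pathway System". Section 10.2 describes two kinds of behavioral measure:

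- **Capsaicin-heat ratings.** Capsaicin is described as applied once and removed after 30 minutes. On the heat level: "This temperature, individualized for each participant at baseline using the PEST procedure, will be administered throughout the experiment". Twelve blocks are given in a baseline scan, twelve after sham and twelve after real, 36 in all. There is one baseline scan, and no separate pre-scan for each condition.
- **QST.** The ten trials are run before and after each scanning block, so each condition has its own pre and post values.

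The behavioral analysis in 12.0 begins "The behavioral pain measures will be examined using a repeated measures ANOVA with time and condition (LIFUP, sham". The model in full is a "repeated measures ANOVA with time and condition (LIFUP, sham) as between group variables", followed by "These will be paired data within each subject". Neither 12.0 nor 12.1 mentions order, period or sequence, and 'time' is not defined. No effect size, SD, alpha or power is stated for the pain test. The sample size is 20 in 10.1 and 35 in 6.0.

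**The concern.** The design balances order, but the stated model names nothing that uses it. One fixed temperature is applied for the whole experiment after one capsaicin application. On the timings in 10.1, the two condition scans start at least about 30 minutes apart (20 minutes of rest plus 10 minutes of LIFUP). Ratings could move over that interval whatever the treatment.

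If they do, a participant's real-minus-sham difference is raised by the shift in one sequence and lowered by it in the other. Balance makes the shifts cancel in the mean. They do not cancel in the variance, so the standard error of the LIFUP effect grows and a real effect is easier to miss. No power calculation shows a margin that could absorb this.

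The between-group label makes matters worse: taken literally, it discards the pairing that the next sentence of 12.0 asserts.

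**Working it through.** **Inputs from the documents.** N = 20 (10.1) or 35 (6.0); counterbalanced order (10.1); one baseline scan and one scan per condition for the capsaicin-heat ratings (10.2). There is no stated power figure to reproduce.

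**Assumptions.** Two-sided alpha 0.05; sequences split 10/10 or 18/17; no carry-over; true effect set so that a paired t-test has 80% power without drift, which gives 0.66 SD at N=20 and 0.487 SD at N=35. The shift delta between the first and second condition scans is in SDs of the paired difference and is tried at 0.25, 0.5 and 1.0.

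**Step 1: does the baseline scan remove the shift?** No. (real − baseline) − (sham − baseline) = real − sham, so the single baseline drops out and the shift remains.

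**Step 2: model.** For participant i, d = real − sham = tau + s·delta + error, with s = +1 in one sequence and −1 in the other, and error SD 1.

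- Without a period term: mean of d, N−1 df, expected variance about 1 + delta²·N/(N−1). At N=20 this is 1.066, 1.263 and 2.053, so the standard error grows by a factor of about 1.03, 1.12 and 1.43 (square roots).
- With a period term: average of the two sequence means of d, pooled within-sequence variance, N−2 df. The shift drops out.

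**Step 3: simulated power** (200,000 replicates per setting; repeat runs agree to about one percentage point).

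| delta | N=20, no term | N=35 (18/17), no term | either N, with term |
|---|---|---|---|
| 0 | 80% | 80% | 80% |
| 0.25 | 78% | about 80% | 80% |
| 0.5 | 72% | 75% | 80% |
| 1.0 | 50% | about 56% | 80% |

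Type I error at N=20 without the term is 4.4%, 2.9% and 0.6% for the three shifts. With the term it stays near 5%.

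The N=35 column takes the one surplus participant to be in the sequence where the shift adds to the effect. Rerunning the same simulation with the sign of the shift reversed gives 77%, 70% and 44%.

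Hand check at N=20, delta = 1: SE = √(2.053/20) = 0.320; critical difference = 2.093 × 0.320 = 0.671; the estimate itself has SD 1/√20 = 0.224; (0.66 − 0.671)/0.224 = −0.05, or about 48% power. This is close to the simulated 50%.

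**Step 4: bias.** Bias of the unadjusted mean = delta·(n1 − n2)/(n1 + n2). It is zero at 10/10, delta × 1/35 = 0.03 delta at 18/17, and delta × 4/20 = 0.20 delta at an assumed 12/8.

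**Step 5: cost of the term when there is no drift.** At N=20, power is 79.6% with it and 79.8% without.

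**Step 6: the between-group label taken literally** (N=20, no drift). Treating the two conditions as independent groups cuts power from 80% to 70%, 54%, 27% and 10% at assumed within-subject correlations of 0.3, 0.5, 0.7 and 0.8.

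**The case against.** - **'Time' may already be the period term.** If it means scan position and is fitted additively with condition within subject, the shift is removed. A full time-by-condition factorial within subjects could not be fitted, because each participant supplies only two of the four cells, but additive effects are estimable across the two sequences. This stands: a reader might infer that the model certainly lacks a period term, and the text does not establish that. The other natural readings, pre/post or the twelve trials within a scan, leave period unmodelled for the capsaicin-heat ratings.
- **QST may not need it.** If the QST test is pre/post change by condition, a constant level shift between blocks cancels. This stands and confines the point mainly to the capsaicin-heat ratings.
- **The drift is assumed.** The documents give no figure, and 10.2 says that stimuli rated 7 out of 10 give very repeatable ratings. This stands as a limit on size. That statement carries no number, however, and does not say that ratings hold level over this session.
- **The interval is unsettled.** Section 5.0 pays for scanning sessions at Visits 2 and 3, and 7.0 describes targeting at both, while 10.1 has one session and 16.0 a single scan. LIFUP lasts 10 minutes per condition in 10.1 and 20 in 10.3. Separate visits would change where a period effect comes from, but would not remove the case for the term.
- **The test remains valid.** A reader might infer a biased estimate or excess false positives. With balanced order neither follows: the estimate is unbiased and the type I error falls. Bias at 18/17 is trivial, and the 12/8 split is an illustration, since no dropout figure is given.

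**Conclusion.** The point holds in a limited form. Section 12.0 names no period or sequence term for a counterbalanced crossover, leaves 'time' undefined, and gives paired factors a between-group label. Unless 'time' is scan position, drift between the two condition scans widens the error of the capsaicin-heat comparison.

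The size cannot be fixed from the documents. Under the stated assumptions the loss at N=20 is about 2, 8 and 30 percentage points at shifts of 0.25, 0.5 and 1.0 SD. At N=35 it is about 0, 5 and 24 points, or 3, 10 and 36 if the surplus participant falls in the other sequence.

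Two stronger readings are not supported. One is that the trial's primary test is known to be underpowered for this reason: 12.0 designates no single primary test and states no target power. The other is that a second-level real-versus-sham imaging model is wrong: 12.1 describes task-versus-rest contrasts and group activation and states no such comparison. Severity is moderate. The change is worth making because it costs almost nothing, not because the present test is invalid.

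**What to change.** In 12.0:

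1. Define 'time' separately for QST and for the capsaicin-heat ratings.
2. Declare condition and time as within-subject factors and delete the between-group label.
3. Analyse the capsaicin-heat ratings as a two-period crossover, with condition, period and sequence as fixed effects and participant as random. With complete data this equals the average of the two sequence means of real minus sham, with pooled within-sequence variance and N−2 df.
4. For QST, state whether the test is pre/post change by condition. If it is not, add the period term there too.
5. If a second-level real-versus-sham fMRI contrast is run, say so in 12.1 and include sequence in it.

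Reconcile 5.0 and 7.0 with 10.1 and 16.0 on one session or two visits, and 10.1 with 10.3 on LIFUP duration, since these decide what the periods are and how far apart they lie. Settle the model before unblinding, because adding the term after seeing results would be a post hoc choice.

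The cost is wording and one degree of freedom. No new data are needed, provided each participant's assigned order is kept in the analysis file. The term does not address carry-over from real LIFUP into a later sham scan, which is a separate question.
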